4.6.5.1.2. Pancreatitis Events

Summaries of adjudicated and investigator-reported pancreatic events will be provided by treatment. Detailed searching criteria can be found in Appendix 6.6 (Section 6.6).

Treatment emergent adjudication-confirmed pancreatitis will be considered as an AESI. Listing of participants with adjudicated pancreatitis may be provided if deemed necessary.

4.6.5.2. Gastrointestinal Safety

4.6.5.2.1. Nausea, Vomiting, and Diarrhea

Summaries and analyses for incidence and severity of nausea, vomiting (including “vomiting” and “vomiting projectile”), diarrhea (including “diarrhea” and “diarrhoea”), and 3 events combined, will be provided by each treatment group.

Summary of the prevalence over time for nausea, vomiting, and diarrhea will also be presented.

Time to the first onset of nausea, vomiting, and diarrhea will be plotted.

4.6.5.2.2. *Severe Gastrointestinal Events*

Severe GI AEs will be captured with the AE-CRF form and serious cases will be captured with the SAE form. The PTs in the GI SOC MedDRA version at the time of database locks will be used to identify GI AEs, and only the PTs with severe/serious treatment-emergent cases will be considered as AESIs.

The counts and percentages of participants with severe/serious treatment-emergent GI events will be summarized by treatment.

4.6.5.3. **Hepatobiliary Disorders**

4.6.5.3.1. *Hepatic Events*

Severe/serious treatment-emergent hepatic events will be considered as AESI and summarized. The counts and percentages of participants with treatment-emergent potentially drug-related hepatic events will be summarized by treatment using the MedDRA PTs. Detailed searching criteria can be found in Appendix 6.6 (Section 6.6).

4.6.5.3.2. *Acute Gallbladder Disease*

Events related to acute gallbladder disease will also be summarized by treatment groups by PT with decreasing frequency. Detailed searching criteria can be found in Appendix 6.6 (Section 6.6).

Severe/serious acute gallbladder disease will be considered as AESIs and summarized separately.

4.6.5.3.3. *Liver Enzymes*

Common analyses for laboratory analyte measurements described in Section 4.6.3.6 are applicable for the liver enzyme related measurements. This section provides additional analyses for liver enzymes.

The counts and percentages of participants with the following elevations in hepatic laboratory tests at any time during the treatment period and during the entire study including safety follow up period will be summarized between treatment groups:

- The counts and percentages of participants with an ALT measurement ≥ 3 times ($3\times$), 5 times ($5\times$), and 10 times ($10\times$) the central lab ULN will be summarized for all participants with a postbaseline value and for subsets based on various levels of baseline value.
 - participants whose nonmissing maximum baseline value is $\leq 1\times$ ULN
 - participants whose maximum baseline is $>1\times$ ULN, and
 - participants whose baseline values are missing.
- The counts and percentages of participants with an AST measurement $\geq 3\times$, $5\times$, and $10\times$ the central lab ULN will be summarized for all participants with a postbaseline value and for subsets based on various levels of baseline value, as described above for ALT.
- The counts and percentages of participants with a TBL measurement $\geq 2\times$ the central lab ULN will be summarized for all participants with a postbaseline value, and for subsets based on various levels of baseline value:

- participants whose nonmissing maximum baseline value is $\leq 1 \times$ ULN
 - participants whose maximum baseline is $> 1 \times$ ULN, but $< 2 \times$ ULN
 - participants whose maximum baseline value is $\geq 2 \times$ ULN, and
 - participants whose baseline values are missing.
- The counts and percentages of participants with a serum ALP measurement $\geq 2 \times$ the central lab ULN will be summarized for all participants with a postbaseline value and for subsets based on various levels of baseline value, as described above for TBL.

Maximum baseline will be the maximum nonmissing observation in the baseline period. The maximum postbaseline value will be the maximum nonmissing value from the postbaseline period. Scheduled and unscheduled measurements will be included.

4.6.5.4. Hypoglycemia

The following categories in accordance with the 2020 American Diabetes Association position statement on glycemic targets (ADA 2020) will be defined in the database.

Glucose alert value (Level 1):

- **Documented symptomatic hypoglycemia** is defined as any time a patient feels that he/she is experiencing symptoms and/or signs associated with hypoglycemia and has a BG level of < 70 mg/dL (< 3.9 mmol/L).
- **Documented asymptomatic hypoglycemia** is defined as any event not accompanied by typical symptoms of hypoglycemia, but with a measured BG < 70 mg/dL (< 3.9 mmol/L).
- **Documented unspecified hypoglycemia** is defined as any event with no information about symptoms of hypoglycemia available, but with a measured BG < 70 mg/dL (< 3.9 mmol/L).

Documented Clinically Significant Hypoglycemia (Level 2):

- **Documented symptomatic hypoglycemia** is defined as any time a participant feels that he/she is experiencing symptoms and/or signs associated with hypoglycemia and has a BG level of < 54 mg/dL (< 3.0 mmol/L).
- **Documented asymptomatic hypoglycemia** is defined as any event not accompanied by typical symptoms of hypoglycemia but with a measured BG < 54 mg/dL (< 3.0 mmol/L).
- **Documented unspecified hypoglycemia** is defined as any event with no information about symptoms of hypoglycemia available but with a measured BG < 54 mg/dL (< 3.0 mmol/L).

Severe Hypoglycemia (Level 3):

- **Severe hypoglycemia** is defined as an episode with severe cognitive impairment requiring the assistance of another person to actively administer carbohydrate, glucagon, or other resuscitative actions. These episodes may be associated with sufficient neuroglycopenia to induce seizure or coma. Plasma glucose measurements may not be available during such an event, but neurological recovery attributable to the restoration of PG to normal is considered sufficient evidence that the event was induced by a low PG concentration.

Other hypoglycemia categories:

- **Nocturnal hypoglycemia** is defined as any hypoglycemic event that occurs between bedtime and waking.

To avoid duplicate reporting, all consecutive hypoglycemic events occurring within a 1-hour period will be considered as a single hypoglycemic event.

Statistical summaries and analyses will exclude hypoglycemic events occurring after initiation of rescue antihyperglycemic medication. Both the incidence (percent of participants experiencing ≥ 1 episode) and the rate (episodes/participant/year) of level 2 or level 3 hypoglycemia, and level 3 hypoglycemia will be reported by treatment group.

The incidence of hypoglycemic events will be analyzed using logistic regression with treatment and stratification factors as fixed effects. The rate of hypoglycemic episodes per patient year may be analyzed using a generalized linear mixed-effects model assuming the number of hypoglycemic episodes follows a negative binomial distribution with the mean modeled using stratification factors and treatment as fixed effects. When the number of hypoglycemic events is less than 10, a listing of hypoglycemic events will be provided instead.

[figure not shown]
If a hypoglycemic event meets the criteria of severe, the event would specifically be collected as an SAE. Serious hypoglycemia is defined by pharmacovigilance criteria and will also be captured with an SAE form.

Severe/serious hypoglycemia will be considered as AESIs. The summaries of severe/serious hypoglycemia will be provided by treatment group. A listing of all events of severe/serious hypoglycemia may be provided, if deemed necessary. This listing will provide treatment allocation, clinical characteristics of the hypoglycemic event, and concomitant antihyperglycemic medications.

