8.3.2. Special Safety Topics

8.3.2.1. Hypoglycemia

Upon ICF signing, all participants will be educated about signs and symptoms of hypoglycemia, how to treat hypoglycemia, and how to collect appropriate information for each episode of hypoglycemia.

Participants who develop persistent or recurrent unexplained hypoglycemia during the treatment period will be asked to reduce the dose or discontinue any concomitant AHMs commonly associated with hypoglycemia (for example, sulfonylurea).

All hypoglycemic episodes will be recorded on a specific eCRF (Hypoglycemic Events eCRF) and should not be recorded on the AE eCRF, unless the event meets serious criteria. If a hypoglycemic event meets severe criteria (see definition below), it should be recorded as serious on the AE and SAE eCRFs, and reported to Lilly as an SAE. All post-treatment hypoglycemic events collected on the hypoglycemic eCRF will be considered as treatment-emergent and included in the analysis of incidence and rate of hypoglycemic events.

Investigators should use the following definitions and criteria when diagnosing and categorizing an episode considered to be related to hypoglycemia (the BG values in this section refer to values determined by a laboratory or International Federation of Clinical Chemistry and Laboratory Medicine blood-equivalent glucose meters and strips) in accordance with the 2020 American Diabetes Association position statement on glycemic targets (ADA 2020):

Glucose alert value (Level 1):

- **Documented symptomatic hypoglycemia** is defined as any time a participant feels that he or she is experiencing symptoms and/or signs associated with hypoglycemia and has a BG level of <70 mg/dL (<3.9 mmol/L).

- **Documented asymptomatic hypoglycemia** is defined as any event not accompanied by typical symptoms of hypoglycemia but with a measured BG <70 mg/dL (<3.9 mmol/L).
- **Documented unspecified hypoglycemia** is defined as any event with no information about symptoms of hypoglycemia available but with a measured BG <70 mg/dL (<3.9 mmol/L).

Clinically significant hypoglycemia (Level 2):

- **Documented symptomatic hypoglycemia** is defined as any time a participant feels that he or she is experiencing symptoms and/or signs associated with hypoglycemia and has a BG level of <54 mg/dL (<3.0 mmol/L).
- **Documented asymptomatic hypoglycemia** is defined as any event not accompanied by typical symptoms of hypoglycemia but with a measured BG level <54 mg/dL (<3.0 mmol/L).

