9.4. Statistical Analyses

9.4.1. General Considerations

Statistical analysis of this study will be the responsibility of Lilly or its designee. Any change to the data analysis methods described in the protocol will require an amendment ONLY if it changes a principal feature of the protocol. Any other change to the data analysis methods described in the protocol, and the justification for making the change, will be described in the SAP or the clinical study report (CSR). Additional exploratory data analyses may be conducted as deemed appropriate.

Unless otherwise noted, all tests of treatment effects will be conducted at a 2-sided alpha level of 0.05, and the confidence interval will be given at a 2-sided 95% level. In statistical summaries and analyses, data will be analyzed as randomized.

Unless specified otherwise, efficacy analyses will be conducted using efficacy analysis set (EAS) and safety analyses will be conducted using safety analysis set (SS). Baseline is defined as the last nonmissing data collected prior to or at randomization.

Summary statistics for continuous measures will include sample size, mean, SD, median, minimum, and maximum. The analysis model to make comparisons among treatment groups relative to continuous measurements assessed over time will be a mixed model for repeated measures (MMRM), with terms of treatment, visit, treatment-by-visit interaction, stratification factors and baseline measurement as a covariate. An unstructured covariance structure will model relationship of within-patient errors.

Kaplan-Meier method will be used for estimation of cumulative event-free survival rates over time, and cox proportional hazards regression analysis will be used to compare hazard rates among treatments.

Summary statistics for categorical measures (including categorized continuous measures) will include sample size, frequency, and percentages. Logistic regression will be used to examine the treatment difference in binary efficacy outcomes if there is a need to adjust for covariates. Otherwise, Fisher's exact test will be used to examine the treatment difference in categorical outcomes.

Summary statistics for discrete count measures will include sample size, mean, SD, median, minimum, and maximum. The negative binomial regression model will be used for the treatment comparison of discrete count measures.

Other statistical methods may be used, as appropriate, and details will be described in the SAP.

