9.4.4.4.5. Hypoglycemic Events

Incidence and rate of documented symptomatic hypoglycemic events and severe hypoglycemia will be summarized and compared between tirzepatide doses and placebo.

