4.9. Changes to Protocol-Planned Analyses

To provide data on efficacy of the investigational product that would be valuable to better inform clinical decisions in management of people living with obesity and T2DM, protocol-planned objectives are changed as below.

Key secondary objectives

- Added the key secondary objectives of “Demonstrate that tirzepatide 10 mg and/or 15 mg QW are superior to placebo for the percentage of participants who achieve $\geq 20\%$ body weight reduction from randomization at 72 weeks”.
- Changed the objectives “Demonstrate that tirzepatide 10 mg and/or 15 mg QW are superior to placebo for percentage of participants who achieve the target value of HbA1c $\leq 6.5\%$ and $< 5.7\%$ at 72 weeks” from additional secondary objectives to key secondary objectives.

- Added the key secondary objectives of “Demonstrate tirzepatide QW (all doses combined) is superior to placebo for change in HDL-cholesterol (mg/dL) and non-HDL-cholesterol (mg/dL).”
- Changed the objectives of “Demonstrate tirzepatide QW (all doses combined) is superior to placebo for change in total cholesterol (mg/dL), low-density lipoprotein cholesterol (LDL-cholesterol) (mg/dL)” from the key secondary objectives to additional secondary objectives.

Additional secondary objectives

- Added the objective of “Demonstrate tirzepatide 10 mg and/or 15 mg QW are superior to placebo in change from randomization for 7-point self-monitored blood glucose profiles at 72 weeks” as an additional secondary objective.
- Added the objective of “Demonstrate tirzepatide 10 mg and/or 15 mg QW are superior to placebo in change from randomization for EQ-5D-5L utility score and VAS score at 72 weeks” as an additional secondary objective.

5. Sample Size Determination

Approximately 1300 participants will be screened to achieve 900 randomly assigned to study intervention (300 participants per intervention group).

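### The SAP drops hypoglycemic events after rescue that the protocol says to include, does not record the change, and gives the hypoglycemia rate no person-time matched to the events counted

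*SAP*

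**What the plan says.** **Protocol.** Section 8.3.2.1 sends hypoglycemic episodes to a dedicated eCRF; they "should not be recorded on the AE eCRF, unless the event meets serious criteria". The same section then fixes what is analysed: "All post-treatment hypoglycemic events collected on the hypoglycemic eCRF will be considered as treatment-emergent and included in the analysis of incidence and rate". It names no exception for rescue. Section 9.4.4.4.5 plans the comparison, "Incidence and rate of documented symptomatic hypoglycemic events and severe hypoglycemia will be summarized and compared between tirzepatide doses and placebo", and is also silent on rescue. Section 9.4.1 allows changes that do not touch a principal feature to be made without an amendment, provided the change and its reason are given in the SAP or the CSR.

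**SAP.** Section 4.6.5.4 states: "Statistical summaries and analyses will exclude hypoglycemic events occurring after initiation of rescue antihyperglycemic medication". It then promises incidence and a rate in episodes per participant-year "of level 2 or level 3 hypoglycemia, and level 3 hypoglycemia will be reported by treatment group". Incidence is analysed by logistic regression. The rate may be modelled as negative binomial with treatment and stratification factors; no person-time or offset is given there. Severe or serious events are AESIs: "The summaries of severe/serious hypoglycemia will be provided by treatment group".

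Section 4.6 counts safety events by default from first dose to the end of study participation. Under section 4.1 that end is Visit 801 for a participant who completes the study. The general rate model in 4.6 carries an offset of log days in an *active treatment period*, a term the SAP does not define. The SAP's introduction refers the reader to section 4.9 for changes to planned analyses. Section 4.9 opens with "protocol-planned objectives are changed as below" and covers only key and additional secondary objectives. The Version 2 change summary does not mention hypoglycemia.

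**The concern.** There are two separate faults.

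First, the SAP reverses a specific protocol rule on which events enter the incidence and rate analyses, and does not present this as a change. A reader who consults SAP 4.9 would conclude that the protocol rule still stands. Because of the form used for collection, the dropped non-serious events cannot be recovered from the general AE tables.

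Second, a rate is only interpretable if the time at risk covers the window in which events can be counted. Here counting stops at rescue or, failing that, at the end of participation. Nothing in the SAP stops exposure at rescue or ties it to Visit 801. An arm's rate can then be too high or too low, and the comparison between arms shifts if rescue or discontinuation differs by arm.

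**Working it through.** The documents state no hypoglycemia rate or event count, so there is no figure to reproduce. The check compares the texts and then illustrates the window mismatch on assumed values.

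**1. Which events count.** Protocol 8.3.2.1 includes all post-treatment events on the hypoglycemia form; SAP 4.6.5.4 includes only those before rescue. The general safety rules (Protocol 9.4.4; SAP sections 3 and 4.6) keep data after rescue but allow exceptions, so the exclusion does not contradict them. The conflict is with Protocol 8.3.2.1, which has no such allowance.

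**2. Where a post-rescue event would still be seen.**

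| Event after rescue | SAP 4.6.5.4 incidence and rate | General AE tables | SAE table (SAP 4.6.3.2) |
|---|---|---|---|
| Non-serious Level 2 | dropped | absent, not on the AE form | absent |
| Severe or serious | dropped | present | present |

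The SAP does not say whether the exclusion also reaches the severe/serious AESI summaries.

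**3. Windows for the rate.** Events: first dose to the earlier of rescue and end of participation. For a completer without rescue this is 72 + 4 = 76 weeks (Protocol 4.1; SAP 4.1 and 4.6). Exposure: unnamed in 4.6.5.4. The offset in 4.6, read as the treatment period, gives 72 weeks and is not shortened by rescue.

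**4. Illustration.** Assumptions: constant event rate, no dropout, *active treatment period* = 72 weeks, and a share r of an arm rescued at a common week w. The reported rate is the true rate times

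m = [(1 − r) × 76 + r × w] / 72.

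| r | w | m |
|---|---|---|
| 0 | – | 76/72 = 1.056 |
| 0.01 | 24 | 75.48/72 = 1.048 |
| 0.01 | 36 | 75.60/72 = 1.050 |
| 0.03 | 24 | 74.44/72 = 1.034 |
| 0.03 | 36 | 74.80/72 = 1.039 |
| 0.10 | 24 | 70.80/72 = 0.983 |
| 0.10 | 36 | 72.00/72 = 1.000 |
| 0.30 | 24 | 60.40/72 = 0.839 |
| 0.30 | 36 | 64.00/72 = 0.889 |

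The tirzepatide/placebo rate ratio is multiplied by m(tirzepatide)/m(placebo). With 10% or 30% rescued on placebo, 1% or 3% on tirzepatide, and the same week in both arms:

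- smallest: 0.10 versus 0.03 at Week 36, 74.80/72.00 = 1.039
- largest: 0.30 versus 0.01 at Week 24, 75.48/60.40 = 1.250
- equal r and w in both arms: 1.000

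**5. Second form of the check.** Leave out the follow-up weeks and let f be the share of the period after rescue. Each arm's factor is 1 − r × f. Over placebo r of 0–0.30, tirzepatide r of 0–0.05 and f of 0.25–0.67, the ratio factor runs from (1 − 0.05 × 0.67)/1 = 0.967 to 1/(1 − 0.30 × 0.67) = 1.252.

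**6. After repair.** If exposure ends where counting ends, the denominator in step 4 becomes (1 − r) × 76 + r × w, and m = 1.00 in every arm.

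Incidence has no exposure term, so only the choice of events in step 1 affects it.

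**The case against.** *The first fault is one of documentation.* SAP 4.6.5.4 states the exclusion openly, Protocol 9.4.1 does not require an amendment for it, and the reason may still appear in the CSR. Leaving out events after rescue is also a recognisable choice: rescue can include basal insulin, and the SAP applies the same cut to its glycemic efficacy endpoints. The CSR route is indeed open. But neither document offers this reason for hypoglycemia, and it would be met only in part: under Protocol 6.5.3.1, glucose-lowering drugs started after permanent discontinuation of study drug or during safety follow-up are not classed as rescue, so events after those stay in. The result also differs in substance from what the protocol promises.

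*No text makes the section 4.6 offset the hypoglycemia denominator.* Section 4.6.5.4 sets out its own model without reference to it, and section 4.6.1 defines two durations that could serve, one of which runs to the last visit and would remove the 76/72 difference. This is fair as to which denominator was intended. But neither duration is linked to the rate and neither ends at rescue, so the mismatch at rescue remains under every candidate in the SAP.

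*The rate may hardly be used.* The model is optional, and with fewer than 10 events a listing replaces the analysis. This limits the consequence, particularly for Level 3. It does not supply a denominator for the rate that is promised.

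*The illustration is not this trial.* It ignores dropout (Protocol 9.2 assumes 25%), uses one rescue week for everyone, and takes rescue shares from outside the documents. This stands: the range is neither an estimate nor a bound. When rescue is more common on placebo, the error also works against tirzepatide by raising its relative rate.

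*Severe events stay visible* in the SAE table, the SAE listing and the narratives. This stands, and it confines the main loss to non-serious Level 2 events.

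**Conclusion.** The concern holds in both parts. Protocol 8.3.2.1 and SAP 4.6.5.4 give opposite rules for post-rescue events, the change is neither listed nor explained, and following the SAP removes non-serious post-rescue Level 2 events from every planned summary table. The reported rate has no person-time defined to match the events counted.

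The size cannot be determined from the documents. On the stated assumptions, an arm's rate is multiplied by 0.84 to 1.06, and the tirzepatide/placebo ratio by 1.04 to 1.25 when rescue is concentrated on placebo. The ratio is unaffected when rescue is the same in all arms. The text conflict and the missing denominator are certain; the numbers only show that the effect need not be negligible. These are safety summaries outside the multiplicity scheme, so no efficacy conclusion is touched. The SAP should nonetheless be corrected.

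**What to change.** 1. In SAP 4.6.5.4, report incidence and rate for all events after first dose regardless of rescue, as the protocol states. If a pre-rescue analysis is kept, show both, say which is the main one, and record the change and its reason in SAP 4.9.
2. In SAP 4.6 and 4.6.5.4, define the rate denominator and the model offset as days over the window in which events are counted: first dose to end of study participation for the all-events analysis, and first dose to the earlier of rescue and end of participation for any pre-rescue analysis. Define or replace *active treatment period*.
3. For clarity, state whether any exclusion applies to the severe/serious AESI summaries.

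The cost is SAP wording and a small programming change. No new data are needed, and no rule for treating participants changes.

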4.1. Overall Design

Study 18F-MC-GPHL is a Phase 3, multicenter, randomized, parallel, placebo-controlled, double-blinded, 72-week study that will investigate the safety and efficacy of treatment with tirzepatide 10 mg and 15 mg QW SC compared with placebo QW SC, in conjunction with a reduced-calorie diet and increased physical activity, on weight management in participants with T2DM who have obesity (body mass index [BMI] ≥ 30 kg/m²) or are overweight (BMI ≥ 27 kg/m²).

Study participants will be randomized in a 1:1:1 ratio (tirzepatide 10 mg QW, tirzepatide 15 mg QW, and placebo). An upper limit of 70% enrollment of women will be used to ensure a sufficiently large sample of men. In addition, an upper limit of 30% enrollment of participants treated with SU will be used to allow sufficient enrollment of participants treated with other antihyperglycemic medications (AHMs).

All participants will undergo a 3-week screening period, a 72-week treatment period (including a 20-week dose escalation and a 52-week dose maintenance period), and a 4-week safety follow-up period.

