6.3. Measures to Minimize Bias: Randomization and Blinding

This is a double-blind, randomized study.

Participants who meet all criteria for enrollment will be randomized to 1 of the study treatment groups at Visit 3. Assignment to treatment groups will be determined by a computer-generated random sequence using an IWRS. Participants will be randomized in a 1:1:1 ratio to receive tirzepatide 10 mg, tirzepatide 15 mg, or placebo.

The randomization will be stratified by country, sex (female, male), and type of AHM used at randomization (classified according to its potential effect on body weight, see table below).

Stratification Based on the Use of Antihyperglycemic Medications

Stratum	Potential Body Weight Effect	Participants to be Included in the Corresponding Stratum
1	Significant weight loss	
 • The use of an SGLT-2 inhibitor alone or in combination with any other AHMs except for an SU or TZD
2	Significant weight gain	
 • The use of an SU alone or in combination with any other AHMs except for an SGLT-2 inhibitor OR 
 • The use of a TZD alone or in combination with any other AHMs except for an SGLT-2 inhibitor
3	Weight neutral and others	
 • Lifestyle management only: no background AHMs OR 
 • Metformin monotherapy OR 
 • The use of an SGLT-2 inhibitor in combination with an SU and/or TZD, with or without other AHMs Note: The body weight effect of SGLT-2 inhibitor may be offset

Stratum	Potential Body Weight Effect	Participants to be Included in the Corresponding Stratum
		
by SU/TZD, and vice-versa, when used in combination.
 
OR
 
 • All other monotherapy (such as glinides and AGIs) or combination therapy which does not fall under stratum 1 or 2

Abbreviations: AGI = alpha-glucosidase inhibitor; AHM = antihyperglycemic medication; SGLT = sodium-glucose cotransporter; SU = sulfonylurea; TZD = thiazolidinedione.

Investigators, site staff, clinical monitors, and participants will remain blinded to the treatment assignments until the study is complete.

Emergency unblinding may be performed through the IWRS. This option may be used ONLY if the participant's well-being requires knowledge of the participant's treatment assignment. All unblinding events are recorded and reported by the IWRS.

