6.5.1. Management of T2DM at randomization

Use of concomitant glucose lowering medications will be permitted at randomization, with the exception of GLP-1R agonist, DPP-4 inhibitors, or other injectable therapies (for example, insulin). **To minimize the risk for hypoglycemia, participants taking insulin secretagogues (for example, sulfonylurea) at randomization should have their dose halved (or stopped if already on the lowest dose) at randomization.** All other AHM will be continued at their current dose at randomization.

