4.3.2.2. The Analysis Related to the Efficacy Estimand

The analysis related to efficacy estimand will be conducted utilizing data in the EAS.

For the mean percent body weight change from randomization, a MMRM will be conducted. REML will be used to obtain model parameter estimates and the Kenward-Roger option will be used to estimate the denominator degrees of freedom. The response variable of MMRM will be the percent change in body weight from baseline values obtained at each scheduled post baseline visit.

For the percentage of participants achieving at least 5% body weight reduction from randomization over time, a logistic regression model will be used with the response variable of achieving at least 5% body weight reduction (Yes or No) at 72-week visit, with missing value imputed using the predicted value from MMRM analysis followed by dichotomization.

For MMRM the independent variables of analysis model are treatment group, visit, treatment-by-visit interaction, stratification factors (type of AHM used at randomization, sex, and country/pooled country) as fixed effects, and baseline body weight as a covariate. An unstructured covariance structure will model relationship of within-patient errors. If this model fails to converge, the following variance covariance structures will be tested in order until convergence is achieved:

- heterogeneous Toeplitz
- heterogeneous first order autoregressive
- heterogeneous compound symmetry
- Toeplitz
- first order autoregressive, and
- compound symmetry.

The first covariance structure that converges will be used.

With the aid of the MMRM analysis, 2-sided 95% CIs for mean percent change in body weight from randomization to the 72-week visit for tirzepatide 10 mg and 15 mg compared to placebo will be derived and summarized. The resulting least squares mean (LSM) estimates of mean percent change in body weight from baseline will be plotted by visit and by study treatment.

With the aid of the logistic regression model, 2-sided 95% CI and odds ratio for percentage of participants achieving at least 5% body weight reduction from baseline to the 72-week visit between tirzepatide 10 mg and placebo, as well as tirzepatide 15 mg and placebo will be derived.

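### The body-weight-based AHM factor in the hypoglycaemia models adjusts only partly for insulin-secretagogue use, and no hypoglycaemia result is planned by secretagogue use

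*SAP*

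**What the plan says.** SAP 4.6.5.4 reports the incidence and rate of level 2 or 3 hypoglycaemia, and of level 3 alone, by treatment group. For incidence: "The incidence of hypoglycemic events will be analyzed using logistic regression with treatment and stratification factors as fixed effects". The rate model is optional and assumes that "the number of hypoglycemic episodes follows a negative binomial distribution with the mean modeled using stratification factors and treatment as fixed effects". SAP 4.3.2.2 spells out the factors: "stratification factors (type of AHM used at randomization, sex, and country/pooled country) as fixed effects".

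Protocol 6.3 builds the AHM factor on potential body-weight effect, in three levels:

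- Stratum 1 holds SGLT-2 inhibitor users without an SU or a thiazolidinedione (TZD).
- Stratum 2 includes "The use of an SU alone or in combination with any other AHMs except for an SGLT-2 inhibitor", and also TZD users without an SGLT-2 inhibitor, who need not take an SU.
- Stratum 3 includes "The use of an SGLT-2 inhibitor in combination with an SU and/or TZD, with or without other AHMs", and also participants on lifestyle management only, on metformin alone, or on other agents such as glinides.

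The protocol treats secretagogues as a hypoglycaemia concern. Section 6.5.1 says that "participants taking insulin secretagogues (for example, sulfonylurea) at randomization should have their dose halved", with the stated aim of reducing hypoglycaemia risk. Sections 6.5.3.2 and 8.3.2.1 give SU as the example of an agent commonly linked to hypoglycaemia.

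**The concern.** The classification suits a body-weight endpoint, and the hypoglycaemia models take it over unchanged. No level of the factor isolates people on an insulin secretagogue. The models have no treatment-by-AHM term, and no output by background therapy is planned. A reader of the study report would see one overall comparison per dose. That comparison cannot show whether an excess on tirzepatide arises only together with a secretagogue or also without one, a distinction that matters in a trial whose protocol takes a secretagogue-specific step at randomization.

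**Working it through.** The documents give no hypoglycaemia rate, effect size or power, so there is no stated figure to reproduce.

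**1. Where secretagogue users fall (Protocol 6.3)**

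| Background therapy | Stratum | Shares the stratum with |
|---|---|---|
| SU, no SGLT-2 inhibitor | 2 | TZD users without SU |
| SU plus SGLT-2 inhibitor | 3 | lifestyle only, metformin only, others |
| Glinide alone | 3 | lifestyle only, metformin only, others |
| Glinide plus SGLT-2 inhibitor, no SU or TZD | 1 | other SGLT-2 inhibitor users |

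**2. How much of SU use the factor captures**

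Share of variance = Σ m_s(v_s − p)² / [p(1 − p)], where m_s is the size of stratum s, v_s is the SU share within it, and p is the overall SU share. The inputs are assumptions: p 20–30%; 10–50% of SU users also on an SGLT-2 inhibitor; 1–5% on a TZD without SU or SGLT-2 inhibitor; 15% in stratum 1.

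- Low end (p = 20%, half of SU users on an SGLT-2 inhibitor, TZD 5%): stratum 2 is 15% of participants, of whom 66.7% take an SU; stratum 3 is 70%, of whom 14.3% do. [0.15(0.667 − 0.2)² + 0.15(0 − 0.2)² + 0.70(0.143 − 0.2)²] / 0.16 = 26%.
- High end (p = 20%, 10% of SU users on an SGLT-2 inhibitor, TZD 1%): stratum 2 is 19%, of whom 94.7% take an SU; stratum 3 is 66%, of whom 3.0% do. The same formula gives 82%.

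Across the range, 67–96% of stratum 2 and 3–23% of stratum 3 are SU users. Adjustment is incomplete but real.

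**3. Effect on the treatment odds ratio**

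Further assumptions: placebo risk in SU non-users 1%, SU odds ratio 5–10, true treatment odds ratio 3, 300 per arm, two arms. Logistic models fitted to the expected cell probabilities give:

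| Model | Treatment odds ratio |
|---|---|
| Treatment + SU use | 3.00 |
| Treatment + AHM stratum (as planned; sex and country left out) | 2.83–2.99 |
| Treatment only | 2.78–2.93 |

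The largest shortfall is (3.00 − 2.83)/3.00, about 6%. The standard error of the log odds ratio differs by about 0.01 at most between the first two models.

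**4. What the overall comparison cannot separate**

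Take SU users at the permitted maximum of 30%. All risks are assumed.

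- Excess only in SU users: SU 4% placebo, 12% tirzepatide; non-SU 0.5% in both. Placebo 0.3×4% + 0.7×0.5% = 1.55%. Tirzepatide 0.3×12% + 0.7×0.5% = 3.95%.
- Excess only in non-users: SU 4% in both; non-SU 0.5% placebo, 3.93% tirzepatide. Placebo 1.55% again. Tirzepatide 0.3×4% + 0.7×3.93% = 3.95%.

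The overall results are identical and the interpretations are opposite. The rates are illustrative; that one overall result cannot distinguish the two patterns does not depend on them.

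**5. What is planned by background therapy**

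- Protocol 9.4.4.4.5 and SAP 4.6.5.4 compare treatment groups only.
- The AHM-type subgroups in Protocol 9.4.7.2 and SAP 4.7.2.1 cover body-weight outcomes only.
- SAP 6.1.3 tabulates baseline AHM and changes to it, not crossed with hypoglycaemia.
- SAP 4.6.5.4 has an optional listing of severe or serious events that shows concomitant AHMs. It omits level 2 events that are neither severe nor serious.
- The listing used when there are fewer than 10 events has no stated content.

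**The case against.** The case against is strong on the modelling side. Stratum 2 takes in every SU user not on an SGLT-2 inhibitor and stratum 1 has none, so a reader who inferred that the models make no adjustment for SU would be wrong. Treatment is randomised, so partial adjustment does not confound the comparison, and step 3 shows no material attenuation or loss of precision under the assumptions used.

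Two other inferences are tempting and unsupported. The documents name SU as an example of an agent associated with hypoglycaemia; they do not rank secretagogue use as the main determinant. The protocol also says "an upper limit of 30% enrollment of participants treated with SU will be used", but the reason given is to leave room for participants on other AHMs, not hypoglycaemia.

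It is also fair to say that no stated objective asks for a split by secretagogue use, and that the split would be imprecise. At the 30% cap there are about 90 SU users and 210 non-users per arm. The first pattern in step 4 gives about 4/90 against 11/90 in SU users (Fisher p = 0.10). A smaller excess in non-users, 0.5% against 2%, gives about 1/210 against 4/210 per dose (p = 0.37), or 1/210 against 8/420 with doses pooled (p = 0.28). Finally, Protocol 6.5.1 and 6.5.3.2 provide for secretagogues to be reduced or stopped at or after randomization, so a baseline flag will count as users some people who no longer take one.

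These points limit what the table can prove. They do not remove the reason for it: the overall estimate carries no information on the question, and a descriptive split carries some.

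**Conclusion.** The concern holds as a reporting gap with a minor modelling component. The AHM factor is a partial proxy for SU use (26–82% of its variance under the assumed mixes), and no planned table, subgroup or guaranteed listing shows hypoglycaemia by secretagogue use. The planned treatment comparison is valid; its odds ratio is at most about 6% below the SU-adjusted value under the assumptions in step 3. What is lost is the ability to see whether any excess occurs with a secretagogue, without one, or both. The placement of SU users and the missing output can be read directly from the documents. Every percentage for treatment mix, risk and odds ratio is an assumption, apart from the 30% cap. This is an inexpensive and worthwhile addition, not the correction of a wrong estimate.

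**What to change.** In SAP 4.6.5.4:

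1. Report incidence and rate of level 2 or 3 hypoglycaemia by treatment (placebo, each dose, and pooled tirzepatide) within baseline insulin-secretagogue use (SU or glinide, yes/no), descriptively where events are few. This is the essential part.
2. Add the same yes/no variable to the incidence and rate models alongside the stratification factors. It should not replace the AHM stratum, because that would drop a randomisation factor from the model.
3. Footnote the table to say that the flag is fixed at baseline and does not reflect secretagogue reduction or stopping at or after randomization.

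The cost is SAP wording, one table and one model term. Baseline AHM is already collected, SAP 2.1 makes no multiplicity adjustment for safety assessments, and trial conduct does not change. The downsides are small event counts in some cells and the imprecise flag noted in item 3.
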